4.4.2. Secondary Efficacy Variables

ORR by investigator assessment is determined by the proportion of patients with best overall response of CR or PR based on investigator-assessed evaluation..

Duration of response (DOR) is determined for patients with BOR of CR or PR. DOR is measured from the time measurement criteria are first met for CR/PR (whichever is first recorded) until the first date of recurrent or progressive disease (photographic or radiographic), or death due to any cause.

- Patients who do not have a documented tumor progression or death will be censored at the last evaluable tumor assessment.
- Patients who do not have a documented tumor progression or death before initiation of new anti-cancer therapy will be censored at the last evaluable tumor assessment prior to or on the date of new anti-cancer therapy.
- Patients who do not have any evaluable post-baseline tumor assessment and do not die will be censored on the date of first study treatment.

Progression-free survival (PFS) is measured from the start of treatment until the first date of recurrent or progressive disease (photographic or radiographic), or death due to any cause.

- Patients who do not have a documented tumor progression or death will be censored at the last evaluable tumor assessment.
- Patients who do not have a documented tumor progression or death before initiation of new anti-cancer therapy will be censored at the last evaluable tumor assessment prior to or on the date of new anti-cancer therapy.
- Patients who do not have any evaluable post-baseline tumor assessment and do not die will be censored on the date of first study treatment.

Overall survival (OS) is measured from the start of treatment until death due to any cause. Patients who do not die will be censored at the last date that patient is documented to be alive. As many patients may receive new anti-cancer therapy after disease progression, a sensitivity analysis of OS will be conducted by censoring patients at the first date of a new anti-cancer therapy is taken.

Time to tumor response (TTR) is determined for patients with BOR of CR or PR. TTR is measured from the start of treatment until the time measurement criteria are first met for CR/PR (whichever is first recorded).

For all of the above time-to-event variables, the time to event (day) is the date of event/censor - the date of first study treatment + 1.

CR rate is determined by the proportion of patients with best overall response of CR (tumor biopsy confirmation is required for Group 2 patients).

Disease control rate (DCR) is determined by the proportion of patients with BOR of CR, PR, or SD.

Durable disease control rate (dDCR) is defined as the proportion of patients best overall response of CR, PR, or SD without progression for at least 27 weeks (allowing tumor assessment made 1 week earlier than week 27).

Patient-reported quality of life are measured by the EORTC QLQ-C30 (Aronson 1993) and Skindex-16 (Chren 2001) on day 1 of every cycle and at EOT.

- The global health status/QoL, five functional scales (physical, role, cognitive, emotional and social), and three symptom scales (fatigue, pain, nausea and vomiting) and a number of single items assessing additional symptom commonly reported by cancer patients (dyspnoea, loss of appetite, insomnia, constipation and diarrhoea) and perceived financial impact of the disease will be computed using the QLQ-C30 scoring procedures (Fayers 2001).
- The scores for global and three domains of symptoms (4 items), functioning (5 items), and emotions (7 items) will be computed using the Skindex-16 scoring procedures (Chren 2001).
- Change scores are defined as change of summary score of EORTC QLQ-C30 or Skindex-16 from day 1 of first treatment cycle.

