5. At time of progression, the EOS tumor biopsy should be obtained for all patients in Group 2. Blood samples for laboratory tests (hematology, blood chemistry, urine pregnancy test, urinalysis) and immune safety (RF, ANA, TSH, CRP) are also obtained at time of progression (within 28 days of the imaging study that documented progression) according to the EOS assessment schedule (Table 4 and Table 5).
6. Refer to Section 8.2.3.6 for the chemistry panel.
7. Pregnancy tests may be urine β -HCG or serum.
8. Refer to Section 8.2.3.6 for the urinalysis panel.
9. Cemiplimab PK samples will be collected at follow-up visits 1, 4, and 7. ADA samples will be collected at follow-up visits 1 and 7. ADA is not required at the EOS visit if it was collected at follow-up visit 1. PK is not required at the EOS visit if it was collected at follow-up visit 1 and follow-up visit 4.
10. The same method (CT/MRI) and/or digital medical photography used at baseline should be used throughout the study. Scans linked to follow-up visits are required only if PD has not been confirmed previously while on study. CT/MRI imaging will be obtained within 14 days prior to the follow-up visit, so that the disease status is known at the time of the visit. Digital medical photography may be obtained within 14 days prior to visit, or on the day of the visit, and response status (CR, PR, SD, PR) will guide whether the visit is to be treated as a follow-up visit or as the EOS visit.

11. Concomitant medications should be recorded from the date of informed consent through 30 days after last dose of study drug. Any drug started to treat a study drug-related AE during the follow-up will also be recorded. In addition, any cancer treatments should be recorded from the day of informed consent until 105 days (5 half-lives) after the administration of the last dose of cemiplimab. Any AE assessed as related to study treatment and persisting after 105 days (5 half-lives) post last dose should be reported until resolution to baseline or grade ≤ 1 .
12. Nonserious AE and SAE data will be collected from the day of informed consent until 30 days after the last dose of cemiplimab. Any AE assessed as related to study treatment and persisting after 105 days (5 half-lives) post-last dose should be reported until resolution to baseline or grade ≤ 1 .
13. Patients who do not experience PD will be followed for an additional 1 year with assessments every 4 months.

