8.1.4. Follow-up

Patients who discontinue study treatment due to PD should return to the clinic 30 days (range: 21 to 42 days) after the last study treatment to complete the EOS assessments indicated in [Table 4](#) (same as in [Table 5](#)), as appropriate. After the EOS visit, patients with PD should be followed for survival status until death, loss to follow-up, or study termination by the sponsor.

For all patients in Group 2, tumor biopsies ([Appendix 4](#)) should be obtained at time of progression, whether progression occurs in cycles 1 through 9 or during follow-up (after cycle 9).

Patients who discontinue study treatment due to reasons other than PD (eg, toxicity, confirmed CR after 45 weeks) should continue follow-up to complete all assessments in [Table 6](#) until PD or completion of follow-up visits 1 to 7 and extended follow-up ([Table 6](#)). After this time, patients will be followed quarterly for survival and tumor treatment status, if available, until death. Survival follow-up status may be determined at clinic visits or via telephone contact with the patient, a family member of the patient, or the physician.

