10.6. Additional Statistical Data Handling Conventions

The following analysis and data conventions will be followed:

Definition of baseline:

- Unless otherwise specified, the last assessment before the initial administration of cemiplimab will be considered the baseline evaluation

General rules for handling missing data:

- Unless otherwise specified, there will be no imputations for missing data
- If the start date of an AE or concomitant medication is incomplete or missing, it will be assumed to have occurred on or after the intake of study medication, except if an incomplete date (eg, month and year) clearly indicates that the event started prior to treatment. If the partial date indicates the same month or year of the intake of study medication date, then the start date by the study medication intake date will be imputed, otherwise, the missing day or month by the first day or the first month will be imputed.
- Patients who are deemed not evaluable by RECIST version 1.1 (Group 1; [Appendix 1](#)) or by the composite response criteria (Group 2; [Appendix 2](#)) will be considered as not reaching PR/CR for ORR. Their disease progression will be censored at the date of baseline tumor assessment + 1 day. Duration of response and PFS will be censored at the last tumor assessment date for patients without disease progression.
- Missing data in quality of life analysis will be presented as missing in changes scores

Visit windows:

- Assessments taken outside of protocol allowable windows will be displayed according to the CRF assessment recorded by the investigator.

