An independent central review committee, with access to de-identified digital medical photography results and biopsy results, will provide response assessments as required by the sponsor to address study objectives (Section 5.3.3). Central reviews will be scheduled by the sponsor or designee, but will not be continuous or “real-time.” Clinical management decisions generally will be as per investigator response assessments and local pathology review. In the unlikely event that central review yields major differences with the local response assessment that could have implications for the ongoing management of an active patient on study, the situation will be discussed between the sponsor and the investigator in order to determine patient management.

4) Confirmation of Responses

After any objective response, confirmatory digital photography (and radiologic imaging, if performed as part of the initial response assessment) will be obtained at least 4 weeks following initial documentation of objective response.

For any complete responses observed in digital medical photography of externally visible target lesions, confirmatory biopsies are required to establish status of complete response.

5) Patients in Group 1 with Externally Visible Tumors

Regarding Group 1 (metastatic BCC), these patients will generally be followed by RECIST 1.1 criteria (Appendix 1). It is possible that some patients in Group 1 may also have externally visible lesions that are measurable by digital medical photography. In such circumstances, the externally visible lesions generally will be followed as non-target lesions. The exception to this rule would be a patient with externally visible lesions in whom the only M1 lesions are not measurable by RECIST (eg, a patient with bone-only metastases), in which case the externally visible lesions (lesion size ≥ 10 mm in baseline dimensional perpendicular axes) would be target lesions and followed as per clinical response criteria in this appendix, and the non-measurable metastatic lesions (eg, bone metastases) would be followed as non-target lesions. For any target lesions in Group 1 or Group 2 that are measured by digital medical photography, measurements will be bi-dimensional.

6) Patients in Group 2 with Deeply Invasive Tumors

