1.2.2. Secondary Objectives

- To estimate the ORR according to investigator review
- To estimate the duration of response (DOR) and progression-free survival (PFS) by central and investigator review, and overall survival (OS)
- To estimate the complete response (CR) rate by central review
- To estimate the time to tumor response (TTR), disease control rate (DCR), and durable disease control rate (dDCR) by central and investigator review
- To assess the safety and tolerability of cemiplimab
- To assess the pharmacokinetics of cemiplimab (at selective sites only)
- To assess the immunogenicity of cemiplimab
- To assess the impact of cemiplimab on quality of life using EORTC QLQ-C30 and Skindex-16

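### Central-review DOR and PFS are censored informatively when tumor assessments end on investigator-called PD that central review has not called, which biases both estimates upward

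*SAP*

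**What the plan says.** **Who assesses.** Among the secondary objectives in SAP 1.2.2 is "To estimate the duration of response (DOR) and progression-free survival (PFS) by central and investigator review". Protocol 2.2 has the same pair.

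**How patients without an event are handled.** For both endpoints SAP 4.4.2 states: "Patients who do not have a documented tumor progression or death will be censored at the last evaluable tumor assessment". A patient who starts new anti-cancer therapy before a documented progression or death "will be censored at the last evaluable tumor assessment prior to or on the date of new anti-cancer therapy". Protocol 10.6 has a similar rule: "Duration of response and PFS will be censored at the last tumor assessment date for patients without disease progression". None of these sections distinguishes the central from the investigator analysis.

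**Who decides that a patient has progressed.** Protocol 5.1 ends treatment at PD. Appendix 2 (Local Versus Central Review) says: "Clinical management decisions generally will be as per investigator response assessments and local pathology review". It adds that central reviews are scheduled by the sponsor and are not done in real time.

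**What happens after PD.** There is an EOS visit about 30 days after the last dose. Then, per Protocol 8.1.4: "After the EOS visit, patients with PD should be followed for survival status until death, loss to follow-up, or study termination by the sponsor". Footnote 10 to the follow-up schedule (Table 6) says: "Scans linked to follow-up visits are required only if PD has not been confirmed previously while on study".

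**Sensitivity analyses.** SAP 4.4.2 and 5.8.2 plan one for OS only. None is planned for DOR or PFS.

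**The concern.** Kaplan-Meier estimation assumes that a censored patient has the same future risk as those still under observation. Here the event is PD by central review, but the end of observation is set by PD according to the investigator. A patient whom the investigator judges to have progressed is more likely than others to be called PD centrally at the next scan, and for most such patients there is no next scan. The plan does not say how the central analysis treats this patient, so the general rule censors at the last evaluable assessment.

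Disagreement is foreseeable. Under Appendix 5 the investigator outlines palpable as well as visible tumor, while central review works from photographs, scans and biopsy results. Under Appendix 4, local and central pathology read separate adjacent samples of indeterminate tissue.

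ORR is assessed centrally, and in a single-arm trial the duration of those responses is a large part of what makes the ORR interpretable. The data cut is built around DOR, and the SAP's list of changes says follow-up was lengthened after regulatory feedback to capture DOR more stringently.

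**Working it through.** **The plan's own figures.** The documents give no planned DOR or PFS value. The ORR design reproduces: at least 14/50 gives power 85.2%, and at least 24/80 gives 85.5%. Nothing below depends on it.

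**Step 1: follow one patient through the rules.** The investigator calls PD at an end-of-cycle scan and central review does not.
1. Treatment stops, and tumor imaging ends after the EOS or confirmatory scan.
2. If central review calls PD on that last scan, the patient is an event slightly late. This does little harm.
3. If it does not, central PD can no longer be observed. The patient is then (a) censored at the last evaluable assessment; (b) if new therapy starts, censored at the last assessment on or before it, so that a later death is not an event; or (c) if death comes first without new therapy, an event dated at death.

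Outcomes (a) and (b) remove a high-risk patient from the risk set. Outcome (c) dates the event late. Each lengthens the estimate.

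**Step 2: how much the extra scan can add.** In Tables 4 and 5 the end-of-cycle assessment falls 21 days after the cycle's last dose (day 64 after day 43; day 85 after day 64). EOS is nominally 30 days after the last dose, so about 30 - 21 = 9 days after the PD scan. The window in Protocol 8.1.4 (21 to 42 days) makes that 0 to 21 days. The 4-week confirmatory scan after PD is requested in Appendix 1 (RECIST). Appendix 2 asks for confirmation of responses only, and Protocol 8.2.2 asks for confirmation of PD where possible. Central review therefore usually gets about one more look, often an early one.

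**Step 3: size, on stated assumptions.**
- Discordance d (share of investigator PDs not called centrally): 10%, 20%, 30%. Assumed; not in the documents.
- Exponential time to PD with median 7.6, 9.5 or 12 months. The first two are the DOR medians cited for the earlier hedgehog inhibitor; the third is an assumption.
- Scans at weeks 9 to 45 every 9 weeks, at weeks 57 to 93 every 12 weeks, then follow-up scans.
- Comparator: central review with scans continued, where discordant patients reach central PD one or two scans later.

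Simulated 12-month event-free estimates, median 9.5 months, central PD one scan later, deaths ignored (200,000 patients per scenario):

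| d | Extra scan resolves | Scans continued | SAP rule | Excess (points) |
|---|---|---|---|---|
| 10% | none | 47.8% | 51.0% | 3.2 |
| 20% | none | 48.6% | 55.2% | 6.6 |
| 30% | none | 49.3% | 59.5% | 10.2 |
| 10% | half | 47.8% | 48.9% | 1.1 |
| 20% | half | 48.5% | 50.9% | 2.4 |
| 30% | half | 49.2% | 52.8% | 3.6 |

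Across the three medians and a delay of one or two scans, the excess with no rescue is about 2 to 3, 4 to 7 and 7 to 11 points. When later deaths count as events (hazard 0.02 to 0.04 per month), the 9.5-month figures become about 3, 6 and 9 points with no rescue, and about 1, 2 and 3 points with half rescued.

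**Step 4: upper limit.** Take every investigator PD as true and let the extra scan resolve none. The observed event hazard is then (1 - d) times the true one, so S becomes S^(1-d) and the median is multiplied by 1/(1 - d). With S(12) = 0.5^(12/9.5) = 0.417:
- d = 10%: 0.417^0.9 = 0.455, excess 3.8 points; median 9.5/0.9 = 10.6 months
- d = 20%: 0.417^0.8 = 0.496, excess 8.0 points; median 9.5/0.8 = 11.9 months
- d = 30%: 0.417^0.7 = 0.542, excess 12.5 points; median 9.5/0.7 = 13.6 months

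Counting later deaths as events brings these to about 3.7, 7.5 and 11 to 12 points.

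**The case against.** **Assessments do not stop at the PD call.** This stands. Tables 4 and 5 schedule imaging at EOS, Appendix 1 asks for a scan 4 weeks after PD, and Protocol 8.2.2 allows approved treatment beyond progression. A reader might infer from the survival-only follow-up that imaging ends on the day of the PD call. The documents do not support that. The further look reduces the bias but does not remove it.

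**The investigator's call is not the truth.** This stands too. The estimand is PD by central review, so the fair comparator is central review with scans continued. A reader might take the 11 to 12 points of Step 4 as the expected bias. That needs every investigator call to be right and the extra scan never to help, and the documents establish neither.

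**Death is not always the fallback event.** Correct: the new-therapy rule comes first, and SAP 4.4.2 itself expects many patients to receive further therapy after progression. This changes the description of the rule more than the size.

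**Investigator DOR and PFS are also reported.** They are free of this censoring, and a reader can compare the curves. But they change the assessor for every patient, including who counts as a responder and from when, so the gap mixes reader differences with the censoring. The SAP does not present them as a sensitivity analysis.

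**No decision rests on DOR or PFS.** True: only ORR is tested. A reader might infer that the efficacy conclusion is at risk. It is not, because the ORR test does not use these censoring rules.

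The central review charter is not among the documents and may describe the process further. The analysis rule belongs in the SAP in any case.

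**Conclusion.** The point holds in a limited form. Followed as written, the plan censors some patients in central DOR and PFS because the investigator saw progression, and this biases both estimates upward. The direction requires only that such patients have a higher risk of central PD than those still being scanned.

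The size cannot be computed from the documents. At 10% to 30% assumed discordance, with a 9.5-month median and later deaths counted, the 12-month estimate is too high by about 1 to 3 points if the extra scan resolves half the cases. It is too high by up to about 9 to 12 points at 30% discordance if the extra scan resolves none; the upper end takes every investigator PD as true. For scale, at an event-free rate of 40% the binomial standard error is sqrt(0.40 x 0.60/84) = 5.3 points for PFS in 84 patients, and sqrt(0.40 x 0.60/28) = 9.3 points for DOR in 28 responders (35% of 80). The lower range is thus well inside sampling error and the upper range is not. Without the discordance count, a reader cannot tell which applies.

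The primary ORR analysis is unaffected. This is a cheap improvement to the plan, not a flaw in its main conclusion.

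**What to change.** In SAP 4.4.2 and 5.8.2:
1. Keep the central DOR and PFS analyses as they are.
2. Report, by group, the number of patients whose tumor assessments ended on investigator PD without central PD.
3. Pre-specify a sensitivity analysis of central DOR and PFS in which the event is the earliest of central PD, investigator PD that ended tumor assessments, or death. Label it a conservative bound rather than an unbiased estimate, since some of those investigator calls may be wrong.

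The cost is a few lines of SAP text and one extra run on data already collected. Patient management does not change. The downside is that DOR and PFS may look shorter in that analysis; if discordance is low, it will show that the central estimates are robust.

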7.7.2. Surgery

For patients with locally advanced target lesions that are considered unresectable at baseline, but are subsequently deemed resectable during the course of the study due to tumor response to cemiplimab, curative intent surgery may be allowed, but must be discussed with the medical monitor prior to any surgical procedure. (This statement does not apply to patients in emergency life-threatening situations that require immediate surgery). Patients with inoperable BCC at baseline who are rendered operable with clear margins will be deemed to have experienced PR.

If during the course of the study a patient develops new cutaneous lesions that are suspected to be a non-melanoma skin cancer other than BCC (eg, CSCC), removal of the lesion and continued treatment on study may be allowed after discussion with the medical monitor.

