7.7.3. Radiation Therapy

Radiation therapy is not part of the study regimen. Patients for whom radiation therapy is planned are not eligible. If, during the course of the study, a patient develops a symptomatic lesion for which palliative radiation therapy is deemed appropriate by the investigator, this will be deemed PD and generally the patient would be removed from study. Palliative radiation therapy may be allowed in certain circumstances in patients who have been on study for at least 24 weeks (see Section 7.7.1). Such cases must be discussed with the medical monitor prior to any radiation therapy if the investigator feels that restarting cemiplimab after radiation is in the best interest of the patient. The patient will be deemed to have experienced disease progression if radiation therapy is instituted, but will be followed for OS.

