In addition, if all previously inoperable target lesions are rendered operable with clear margins obtained at the time of surgery, this will be considered a PR. If the investigator deems a previously unresectable lesion to be potentially resectable due to response to cemiplimab, the Medical Monitor should be consulted prior to any surgical procedure being performed. A decision will be rendered by the sponsor as to whether the planned surgical intervention is compatible with study requirements. (This statement does not apply to patients in emergency life-threatening situations that require immediate surgery).

C. Ulcerated Lesions

This section only pertains to target lesions that have extensive ulceration at baseline that prevents measurement by the above methods in this appendix. Response criteria are as follows:

- Complete response: re-epithelialization of the entire baseline area of ulceration of target lesion(s), maintained over at least 4 weeks.
- Partial response: there are no criteria for partial response
- Stable disease: not meeting criteria for complete response or progressive disease
- Progressive disease: new ulceration of target lesion(s) not related to (ie, in a location separate from) tissue biopsy or other known trauma, persistent without evidence of healing for at least 2 weeks

D. Non-Target Lesions

Measurements of non-target lesions are not required. The presence, absence, or in rare cases unequivocal progression of these lesions should be noted throughout follow up.

APPENDIX 3: RECOMMENDED DOSE MODIFICATION OR DISCONTINUATION AND SUPPORTIVE CARE GUIDELINES FOR SPECIFIC STUDY DRUG RELATED ADVERSE EVENTS

Section 7.3.2 provides the dose level reductions.

Event(s)	CTCAE v4.03 Grade	Management/ cemiplimab Dosing	Action/Supportive Care Guidelines	Symptoms ^a	Differential Diagnosis

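### Protocol 7.7.3 deems palliative radiation to be progression, but the DOR and PFS rules in SAP 4.4.2 do not carry this over and most naturally censor the patient

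*SAP*

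**What the plan says.** **Protocol 7.7.3.** If a symptomatic lesion is judged to need palliative radiation, "this will be deemed PD and generally the patient would be removed from study". The section then allows palliative radiation in some patients after at least 24 weeks (see also 7.7.1) and ends: "The patient will be deemed to have experienced disease progression if radiation therapy is instituted, but will be followed for OS". Neither sentence is limited to one assessor.

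**Protocol 10.6.** "Duration of response and PFS will be censored at the last tumor assessment date for patients without disease progression". There is no separate rule for new therapy.

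**SAP 4.4.2.** DOR and PFS each run "until the first date of recurrent or progressive disease (photographic or radiographic), or death due to any cause". A patient without documented progression or death "before initiation of new anti-cancer therapy will be censored at the last evaluable tumor assessment prior to or on the date" of the new therapy. Radiation is not mentioned and new anti-cancer therapy is not defined.

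**Assessors.** SAP 1.2.2 wants both endpoints by central and by investigator review. On the central side, Protocol Appendix 2 says: "An independent central review committee, with access to de-identified digital medical photography results and biopsy results, will provide response assessments". Protocol 8.2.2 adds scans, and 5.3.3 leaves the process to charters that are not among the documents. Appendices 1 and 2, which both assessors use, contain no radiation rule.

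**Related text.** SAP 1.2.4 lists only three added endpoints as changes from the protocol. The only time-to-event sensitivity analysis in SAP 5.8.2 is for OS.

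**The concern.** The same patient can be a failure under the protocol and a censored observation under the SAP. Radiation is given mainly for a symptomatic lesion, so a patient censored at that point probably has a worse outlook than those who stay at risk. Kaplan-Meier estimation assumes otherwise, so DOR and PFS would tend to look longer than under the protocol's rule.

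The trial has no control arm to share such a bias. SAP 1.2.5 records that follow-up was extended after regulatory feedback so that duration of response would be captured more stringently. As the text stands, two programmers could derive different DOR and PFS times for the same irradiated patient.

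**Working it through.** **1. Does new anti-cancer therapy include radiation?** Three places suggest that it does.
- SAP 4.3 defines post-treatment anti-cancer therapy to cover procedures and other therapies, not only drugs.
- SAP 5.9.1 adds the word systemic where only systemic therapy is meant; SAP 4.4.2 does not.
- Protocol exclusion criterion 8 is worded so that radiation is one kind of anticancer treatment.

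**2. What happens to a patient irradiated before imaged progression?**

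| Reading of SAP 4.4.2 | Status at radiation | Agrees with Protocol 7.7.3 and 10.6? |
|---|---|---|
| Radiation is new anti-cancer therapy | Censored at last evaluable assessment | No |
| Radiation is not new anti-cancer therapy | Still at risk until imaged progression, death or last assessment | No |
| Progression deemed under 7.7.3 is documented progression | Event, but with no stated date | Yes, apart from the date |

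The SAP's restriction to photographic or radiographic disease weighs against the third reading. If the lesion is itself measured as progression on or before radiation, the documents agree and no issue arises.

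**3. A comparison within the documents.** Protocol 7.7.2 has a parallel rule for surgery: "Patients with inoperable BCC at baseline who are rendered operable with clear margins will be deemed to have experienced PR". That rule was carried into Appendix 2 ("if all previously inoperable target lesions are rendered operable with clear margins obtained at the time of surgery, this will be considered a PR") and into SAP 4.4.1. The radiation rule in the next protocol section was carried into neither.

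**4. Size.** The plan gives no radiation rate and no figure to reproduce, so what follows is illustration.

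*A case that can be checked by hand.* Assume 28 responders, ordinary events at months 2, 3, ..., 9 (eight events), one patient irradiated at month 7.5 whose last assessment was at month 5.5, and all others followed to month 14.
- Radiation counted: 9 of 28 fail by month 12, so S(12) = 19/28 = 0.679.
- Radiation censored at 5.5: four events come first (24/28), then four among the 23 still at risk (19/23). S(12) = 24/28 × 19/23 = 0.708.
- Difference: 3.0 points.

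*Simulation at the design alternatives.* Responders: 0.34 × 50 = 17 in Group 1 and 0.35 × 80 = 28 in Group 2. Assumptions: exponential DOR with the vismodegib medians in Protocol 1.1 (7.6 and 9.5 months), administrative censoring uniform over 6 to 24 months, and one event before month 12 relabelled as radiation and censored 0 to 9 weeks earlier. There were 20,000 replicates per setting.

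| | Group 1 (17) | Group 2 (28) |
|---|---|---|
| Mean 12-month rate, counted | 33.6% | 41.8% |
| Mean 12-month rate, censored | 36.9% | 44.1% |
| Shift | +3.3 points | +2.3 points |
| Sampling SD of the rate | 12.5 points | 10.0 points |
| Mean events before month 12 | 10.7 | 15.3 |

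At the smallest responder counts that meet the ORR criterion (14 and 24), the shifts are about 4.1 and 2.7 points. If the radiation may fall at any event time, the mean shifts are about 2.9 and 1.9 points. In that setting the 12-month rate is unchanged in about 12 to 14% of replicates and falls in about 1%. It falls when radiation comes after month 12 but the censoring date comes before it.

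*More than one patient.* Under constant hazards, if radiation makes up a share s of first terminating occurrences, the median with radiation censored is m/(1 − s). For m = 9.5 months and s = 10%, this is 9.5/0.9 = 10.6 months, and the 12-month rate goes from exp(−12 ln2/9.5) = 41.7% to exp(−0.9 × 12 ln2/9.5) = 45.5%. At s = 5% the median is 10.0 months and at s = 20% it is 11.9. All values of s are assumed.

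**5. Primary endpoint.** The ORR rule does not use the DOR and PFS censoring rules. Its design checks out: 14/50 gives power 0.852 at 34%, and 24/80 gives 0.855 at 35%, both as stated in SAP 2.3.

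**The case against.** The strongest reply is that the SAP does not define documented progression. The first rule in Protocol 7.7.3 attaches progression to the judgement that a symptomatic lesion needs radiation, and that judgement precedes the first fraction. Progression recorded then would be documented before the new therapy began, and the patient would be an event under both documents. This reading is strained by the photographic-or-radiographic restriction but not excluded, so the texts cannot be called flatly contradictory.

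The term new anti-cancer therapy also has contrary signals. The OS paragraph of SAP 4.4.2 speaks of such therapy being taken, which suits a drug, and Protocol 7.7.1 separates agents from focal palliative treatment. Censoring is therefore the natural reading, not a certain one.

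A reader might infer a definite conflict for investigator review and mere ambiguity for central review. The documents do not support that split: 7.7.3 names no assessor, and Appendices 1 and 2 govern both and are silent for both.

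It is also fair that Protocol Section 10 is only a basis for the SAP, so the SAP may refine it, and that DOR and PFS are descriptive, with no hypothesis test. The 0-to-9-week gap in the simulation is simplified too, since assessments are 12 weeks apart from cycle 6. None of this supplies the missing definition, event date or assessor rule.

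**Conclusion.** The point holds as a mismatch that needs to be reconciled. The protocol deems radiation to be progression; the SAP does not carry this into DOR or PFS, and its most natural reading censors the patient. Only a strained reading of documented progression brings the texts together, and even then the event has no date. How the rule applies to either assessor is unstated.

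The size is unknown because no radiation rate is given. One irradiated responder moves the 12-month DOR rate by about 3 points in Group 1 and 2 points in Group 2 on average, against sampling SDs of 12.5 and 10.0 points. These figures rest on the assumed exponential durations, the vismodegib medians and the assumed censoring pattern. Only patients irradiated before imaged progression are affected and, for DOR, only confirmed responders.

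Two stronger conclusions might be inferred and should not be. The shift is not always favourable: it is non-negative when the event falls before month 12, but otherwise can be zero or, rarely, slightly negative. Nor is the efficacy claim at risk, because the ORR test, its thresholds and its power are unaffected. The omission is worth correcting because the correction is cheap and the bias usually runs one way.

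**What to change.** Reconcile Protocol 7.7.1, 7.7.3 and 10.6 with SAP 4.4.2. In SAP 4.4.2:

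1. State whether new anti-cancer therapy includes radiation.
2. Apply the protocol's deemed-progression rule to DOR and PFS with a stated event date (Protocol 7.7.3 gives none), or list the departure in SAP 1.2.4.
3. State the handling separately for investigator and for central review, in line with the central review charter.
4. Report the alternative handling (event versus censored) as a sensitivity analysis for DOR and PFS.

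The cost is a few sentences and a few extra table rows by group and assessor. DOR and PFS may come out slightly shorter. No change to when radiation may be given is proposed.
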